1.0 Funding

Please list the funder of this project. If there is not a funder, please note that your department pays for your time and resources and should be listed here. [\[Click here to enter text.\]](#)

Has this study been disapproved by or withdrawn from any other IRB?

Yes No

If so, please explain: [\[Click here to enter text.\]](#)

*Does this study involve cancer research or cancer-related issues?

Yes No

If yes, indicate the PRMC number: [\[Click here to enter text.\]](#)

2.0 Objectives

Directions: Describe the purpose, specific aims or objectives. Be sure to also include the hypothesis being tested. 12-04-2019 Modification: Adds a 5th data collection point one year after the last described data point (the 24 week post-intervention collection point) Aim 1: Determine whether the 4-week GIFT intervention, compared to a 4-week unstructured journal-only condition, improves grandmothers' [a] mental health (general mental health and depressive symptoms), [b] physical health (self-rated and general health) and [c] family well-being (family functioning) at 2, 12, and 24 weeks post-intervention. Aim 2: Determine if changes in [a] problem solving/coping (resourcefulness), [b] resources (subjective and instrumental social support), and [c] situational appraisals (appraised stress, appraised reward, and depressive cognitions) mediate the relationships between GIFT and individual and family outcomes at 2 weeks, 12 weeks, and 24 weeks post-intervention. Aim 3. Determine if [a] grandmother demographics (age, race, education, marital status, and employment status), [b] caregiving status, and [c] family demands (intra-family strains) moderate the relationship between the intervention and the outcomes in Aims 1 and 2. **COVID-19 Supplemental Survey** – Participants who expressed an interest in future research at the 4th data collection point will be asked by phone or email to participate in a survey asking about their experiences during the covid epidemic. They will be emailed an online consent form that follows the same signing protocol we have used previously with this sample |

3.0 Background

Directions: Describe the relevant prior experience and gaps in current knowledge describing how it will add to existing knowledge. Include any relevant preliminary data. 12-04-2019 Modification: Adds a 5th data collection point one year after the last described data point (the 24 week post-intervention collection point). In 2009, 7.8 million American children age 18 or younger lived with a grandparent, a 64% increase from 1991.116 In most cases, grandmothers are the head of these households, alone or with a spouse. There are two distinct types of such households: grandmothers raising grandchildren whose parents are unable to care for them and grandmothers living in multigenerational homes with grandchildren and their parents. Those who are very involved in caring for their grandchildren are at greater risk of depression and poorer overall health than their non-caregiving peers.³⁻⁵ Many grandmothers living with grandchildren are stressed and depressed,⁶ which has a cascading effect on the family, creating an increased risk for poor

family functioning, especially if the grandmother is raising grandchildren without the children's parents in the home.⁷⁻¹⁰ Most of the relevant research to date has been descriptive and focused on the stress and health risks, particularly depressive symptoms, of raising grandchildren in grandparent-headed homes, although grandmothers in multigenerational households often face complex stresses as well.¹¹⁻¹⁸ Little research, however, has examined interventions to support grandmothers during their caregiving experience. Transitions from lower levels to higher levels of grandchild caregiving (e.g., starting to raise a grandchild or initiating a multigenerational home) are associated with worsening health problems.¹⁹ During and after grandchild caregiving transitions, the presence of positive coping skills and resources, such as resourcefulness and social support, may reduce the negative effects of caregiving and family demands on the well-being of the grandmother and family.^{19,22} Our prior work links greater resourcefulness with fewer depressive symptoms and better health.^{11,23-26} We have shown that face-to-face resourcefulness training in older adults, including grandmothers, improves both mental and physical health.²⁷⁻²⁹ Our descriptive and pilot intervention studies have laid the foundation for grandparent research in the area of resourcefulness,³⁰⁻³⁴ and we propose to apply this knowledge to a widely accessible intervention that reduces stress and health risks. The purpose of this study is to extend our previously successful face-to-face resourcefulness intervention to a web-based format for grandmothers, a population with which our team has considerable experience. The web-based intervention, Grandmother Initiatives in Family Transformation (GIFT), provides online resourcefulness training using structured reflective journaling to reinforce resourcefulness skills. We will conduct a randomized clinical trial (RCT) comparing the health effects of two online conditions: GIFT vs. unstructured journaling alone. Given the limited interventions available to these groups of women, an intervention that transcends time and place and is available 24 hours a day is expected to bolster the personal and social resourcefulness of grandmothers living with and raising grandchildren, which will in turn affect individual and family health outcomes. In this two-group randomized trial, we will randomly assign 320 grandmothers to a web-based (a) GIFT resourcefulness training (n=160) or (b) an unstructured journal-only comparison group (n=160). Grandmothers' demographic characteristics, caregiving status relative to grandchildren (raising grandchildren versus sharing a home with grandchildren and their parents) and family demands (intra-family strain) will serve as covariates. Study aims are: Aim 1: Determine whether the 4-week GIFT intervention, compared to a 4-week unstructured journal-only condition, improves grandmothers' [a] mental health (general mental health and depressive symptoms), [b] physical health (self-rated and general health) and [c] family well-being (family functioning) at 2, 12, and 24 weeks post-intervention. Aim 2: Determine if changes in [a] problem solving/coping (resourcefulness), [b] resources (subjective and instrumental social support), and [c] situational appraisals (appraised stress, appraised reward, and depressive cognitions) mediate the relationships between GIFT and individual and family outcomes at 2 weeks, 12 weeks, and 24 weeks post-intervention. Aim 3. Determine if [a] grandmother demographics (age, race, education, marital status, and employment status), [b] caregiving status, and [c] family demands (intra-family strains) moderate the relationship between the intervention and the outcomes in Aims 1 and 2. Impact Based on our prior research,^{27,32} we hypothesize that the GIFT intervention will facilitate better individual and family outcomes directly, and also indirectly by reducing depressive cognitions and perceived stress, by increasing reward and support, and by buffering the effects of caregiving, family demands and demographic factors on outcomes—mechanisms that will be disentangled in this 4 year randomized trial. If our study validates our hypotheses, the GIFT intervention can provide a low-cost, readily accessible intervention to help grandmothers raising grandchildren to improve their own mental and physical well-being and thereby promote better family well-being, outcomes

that will have long-term individual, family, and societal benefits. Study Design We will conduct a two-group RCT with a longitudinal, multivariate design using a convenience sample of 320 grandmothers living with grandchildren age 16 or under. The RCT will compare GIFT Resourcefulness Training (video plus structured journal to practice resourcefulness skills) to the use of an unstructured journal, which has been found to have a small effect on improving stress and depressive symptoms, but significantly less than the resourcefulness intervention.^{27,52,85} We believe that no “usual care/no-care” control group is necessary to test our hypothesis, given evidence showing the relative stability of the major study variables (physical and mental health, family functioning, resourcefulness, support) over 6.5 years in [name]’s descriptive longitudinal study of grandmothers and over 18 weeks in the control group of [name]’s resourcefulness trial with grandmothers. We will extend the time of follow-up and obtain measures of outcomes, mediating variables, and potential moderating covariates at baseline/pre-intervention (T1) and 2 weeks (T2), 12 weeks (T3), and 24 weeks (T4) post intervention to evaluate early, lagged, and extended effects. |

Please add relevant references at the end of the protocol, not at the end of this section.

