5.0 Number of Research Participants

Directions: Indicate the target number of research participants to be accrued locally, and, if this is a multi-site study, indicate the total number of research participants to be accrued across all sites.

Example language that can be used: *We will enroll 25 subjects at CWRU and plan to enroll 150 subjects study wide.* We will enroll up to 350 participants, recruiting nationally across the United States.

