8.0 Recruitment Methods

Note: Attach all applicable recruitment materials to the last section of the Smart form under "Recruitment Materials."

1. Which of the following methods will be used to recruit research participants. – *Select all that apply*
 Email
 Phone call
 Letter
 Advertisement (e.g., poster, flyer, etc.)
 Social media
 Other. *Please specify:* Click here to enter text.
2. Describe when, where, and how potential research participants will be recruited.
We will seek a national convenience sample of up to 350 grandmothers living with grandchildren, building on strategies we successfully used in our previous research. We will partner with national organizations whose missions support the work of grandparents raising grandchildren and foster intergenerational relationships across various family structures. We have established relationships with several such organizations and will work with them to notify grandmothers who may meet eligibility criteria. Among these groups are Generations United, a national non-profit group focused on intergenerational relationships, and Grandparents.com, with a dedicated section for grandparent caregivers. Both groups reach large audiences of grandparents, health and social service providers, and other consumers. We have a relationship with the Public Children's Services Association of Ohio and their network of national organizations addressing children's needs, including grandparent caregiving (see letters of support). The study will be publicized through each organization's website, printed material, and email, and their network of organizations. In addition, there are over 360 support groups for grandparents in the U.S., most of them focused on raising grandchildren, and we have successfully partnered with support networks in our past recruitment efforts. We will contact these organizations and networks, and they may share both print and electronic advertising materials to inform prospective subjects about the study. Our project manager has organized such recruitment efforts and will lead recruitment all recruitment efforts. In addition, we will register our project at Clinical Trials.Gov and ResearchMatch.org, two online resources that facilitate research-subject recruitment. We will also contact libraries, newspapers, and radio stations as appropriate, and will track subjects' region of the country for purposes of describing the

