12.0 Study Design/Procedures

Directions:

- 1) Describe the overall study design (e.g.: single visit, single-blind, double-blind, non-randomized, randomized, blood draw, investigational drug, device etc.).
- 2) Provide a description of all study-related research procedures being performed, including the length of time involved.
- 3) Include procedures being performed to monitor research participants for safety or minimize risks.
- 4) Describe the source records including medical or educational records, which will be used to collect data about subjects.

Study Design We will conduct a two-group RCT with a longitudinal, multivariate design using a convenience sample of 320 grandmothers living with grandchildren age 16 or under. The RCT will compare GIFT Resourcefulness Training (video plus structured journal to practice resourcefulness skills) to the use of an unstructured journal, which has been found to have a small effect on improving stress and depressive symptoms, but significantly less than the resourcefulness intervention. We believe that no “usual care/no-care” control group is necessary to test our hypothesis, given evidence showing the relative stability of the major study variables (physical and mental health, family functioning, resourcefulness, support) over 6.5 years in [name]’s descriptive longitudinal study of grandmothers¹⁹, 25 and over 18 weeks in the control group of [name]’s resourcefulness trial with grandmothers.²⁷ We will extend the time of follow-up and obtain measures of outcomes, mediating variables, and potential moderating covariates at baseline/pre-intervention (T1) and 2

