16.0 Data Analysis Plan

Directions: Describe the data analysis plan, including any statistical procedures. If applicable, provide a power analysis, and study/safety endpoints. *Statistical Power Analysis for Sample Size Estimation.* For Aim 1, power analysis using G-Power⁴² for RMANOVA testing the interaction between group and time, with an alpha of .05, a power of .80 and a sample size of 250 indicates a detectable small effect size of .07, as was obtained for the social support mediators in our pilot study. The major outcome variables show much larger effects (Figure 3), and therefore, the sample size of 250 is adequate. For Aims 2 and 3, power analyses were conducted applying MacCallum, Browne, and Sugawara's¹¹⁸ calculations to determine sample size for Structural Equation Models. We use the Root Mean Square Error of Approximation (RMSEA) to assess goodness-of-fit of a hypothesized model and the sample data. In testing for power, two hypotheses (close fit and not close fit) are tested. For close fit hypotheses, the higher the power the more likely to reject an incorrect model. For not close fit hypotheses, the higher the power, the more likely to detect a reasonably correct model.¹¹⁸ The difference in two RMSEAs reflects effect size. RMSEAs of .05 (good fit) and .08 (acceptable fit) are used for close fit hypotheses, while .05 (good fit) and .01 (extremely good fit) are used for not close fit hypotheses.¹¹⁸ We constructed a multivariate cross-lagged autoregressive model with four waves of data testing how problem solving/coping, resources, and situational appraisals mediate the impact of the GIFT intervention on the individual and family well-being outcomes.^{34,55-56} Using the sample size of 250 as an estimate for a close fit hypothesis with an alpha of .05, an RMSEA1 of .05, an RMSEA2=.08, and a model with 124 degrees of freedom, the SEM had a power =.996. For a not close fit hypothesis with an alpha of .05, an RMSEA1=.05, an RMSEA2=.01, and a model with 124 degrees of freedom, the SEM had a power =.984. Thus, our final sample of 250 will provide adequate power. **Sample size and attrition.** We will enroll 167 subjects per group to achieve a sample of 125 per group at T4. While our prior longitudinal survey research had a low attrition rate (12%) over 24 months, and our web-based GIFT pilot had 92% continuation at 6 weeks, the face-to-face intervention study²⁷ had 19% loss over 18 weeks, suggesting slightly greater losses by the 24-week follow-up. Therefore, we estimate 25% attrition over the 28 week study duration (intervention plus follow-up) and plan to enroll a total of 334 subjects. Subjects tend to remain in our studies in large part due to their commitment to grandmother caregiving and the team's sensitivity to diversity, which will again be overseen by Co-I [name].

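### The protocol gives two planned sample sizes, 320 and 334; at its own 25% attrition, 320 leaves 240 completers, not the 250 used for power

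*Combined protocol and SAP*

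**What the plan says.** Two different totals appear as the planned sample.

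- Section 3.0 (Background), in the paragraph leading to the aims: "we will randomly assign 320 grandmothers to a web-based (a) GIFT resourcefulness training (n=160) or (b) an unstructured journal-only comparison group (n=160").
- Section 3.0, Study Design paragraph: "We will conduct a two-group RCT with a longitudinal, multivariate design using a convenience sample of 320 grandmothers". Section 12.0 (Study Design/Procedures) carries the same paragraph: "using a convenience sample of 320 grandmothers living with grandchildren age 16 or under". Neither gives a split by arm.
- Section 16.0 (Data Analysis Plan), under sample size and attrition: "We will enroll 167 subjects per group to achieve a sample of 125 per group at T4", and then "we estimate 25% attrition over the 28 week study duration (intervention plus follow-up) and plan to enroll a total of 334 subjects".

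The power statements in section 16.0 all use 250. For Aim 1 the repeated-measures calculation is given "with an alpha of .05, a power of .80 and a sample size of 250 indicates a detectable small effect size of .07". For Aims 2 and 3 the SEM calculation uses 250 with 124 degrees of freedom and reports power of .996 (close fit) and .984 (not close fit).

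A third figure is an upper limit. Section 5.0 says "We will enroll up to 350 participants, recruiting nationally across the United States" and section 8.0 says "We will seek a national convenience sample of up to 350 grandmothers living with grandchildren".

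**The concern.** The planned sample size is the figure against which accrual, retention and the adequacy of the final analysis set are judged. Here two values are stated as firm intentions, each with its own arm size (160 and 167). If enrolment ended between 320 and 334, it could be reported as meeting the plan under one section and missing it under another.

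The two values also differ in what they support. The power case depends on 250 participants at T4. If 320 is the real target, the plan's own attrition allowance does not deliver that number.

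**Working it through.** **Inputs from the documents.** 320 in total, 160 per arm (section 3.0). 167 per group, 334 in total, 25% attrition, 125 per group at T4 (section 16.0). Alpha .05, Aim 1 effect size .07 with stated power .80, N = 250; SEM with 124 degrees of freedom, RMSEA .05 against .08 and .05 against .01 (section 16.0). Four waves, T1 to T4 (sections 3.0 and 12.0).

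**Inputs assumed.** The documents give neither the correlation between repeated measures (rho) nor a sphericity correction. Sphericity is assumed, rho is varied from .3 to .7, and .07 is read as Cohen's f.

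**1. Reproduce the plan's enrolment figure.** 125 / (1 − 0.25) = 166.7, rounded up to 167 per group; 2 × 167 = 334. This matches section 16.0 exactly. Check: 334 × 0.75 = 250.5.

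**2. Apply the same attrition to the other figures.**

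| Enrolled | × 0.75 | Against 250 |
|---|---|---|
| 320 | 240 (120 per arm) | 10 short |
| 334 | 250.5 | met |
| 350 (ceiling) | 262.5 | exceeded |

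Break-even attrition for 320 is 1 − 250/320 = 21.9%.

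**3. SEM power.** The test uses a noncentral chi-square with 124 degrees of freedom and noncentrality (N − 1) × 124 × RMSEA².

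- N = 250: 249 × 124 = 30,876, so noncentrality is 77.2 at RMSEA .05, 197.6 at .08 and 3.09 at .01. Power is .9961 (close fit) and .9835 (not close fit), which reproduces the stated .996 and .984.
- N = 240: 239 × 124 = 29,636, so noncentrality is 74.1, 189.7 and 2.96. Power is .9946 and .9773.

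**4. Aim 1 power.** The group-by-time interaction is tested with a noncentral F. With 2 groups and m = 4 waves, the degrees of freedom are 3 and 3(N − 2), and the noncentrality is f² × N × m / (1 − rho). At f = .07 and rho = .5 this is .0049 × 250 × 4 / .5 = 9.80 for N = 250, and 9.41 for N = 240.

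| rho (assumed) | Power, N = 250 | Power, N = 240 |
|---|---|---|
| .3 | .587 | .568 |
| .4 | .662 | .642 |
| .5 | .749 | .730 |
| .6 | .846 | .830 |
| .7 | .938 | .928 |

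The stated .80 at f = .07 and N = 250 is reproduced at rho = .553; there N = 240 gives .782. Alternatively, at rho = .5 the effect detectable with 80% power is .0740 for N = 250, which rounds to the stated .07, and .0756 for N = 240.

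**5. Can the two totals be reconciled?** One might read 334 as enrolled and 320 as randomised. That does not fit: section 16.0 gives 167 for each group, groups exist only after assignment, and its attrition covers the intervention and follow-up with no separate loss before randomisation. Rounding does not explain the gap either, since section 3.0 gives an exact 160/160 split. The limit of 350 lies above both totals and does not choose between them.

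**The case against.** The best counter-argument is that this is an editorial matter. Only section 16.0 derives a number, and its derivation is correct, so a careful reader would probably take 334 as the calculated target. The Study Design paragraph appears twice word for word, so three mentions of 320 amount to two statements. That paragraph also refers to grandchildren aged 16 or under, whereas the inclusion criteria in section 4.0 say 18 or younger, which suggests text that was never updated. The losses seen in the team's earlier work (12%, 8% and 19%) are all below 25%; at 19%, 320 would leave 259. Section 16.0 also ties the effect of .07 to the social support mediators and expects larger effects on the major outcomes, so the loss on those outcomes would be smaller still.

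Most of this bears on size, and it is right that the size is small. It is also fair that section 16.0 contains no calculation error and that a wide range of rho brings in a separate matter, the unstated correlation.

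The discrepancy remains. Inferring that 334 is probably meant is not the same as the plan saying so, and the only explicit statement of how many will be randomised says 320. Section 16.0 considers the 19% loss over 18 weeks, expects more by the 24-week follow-up, and settles on 25%. Relying on 320 drops that allowance without saying so.

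**Conclusion.** The concern holds. The protocol states two incompatible sample-size targets, and only 334 follows from its own calculation. At the plan's 25% attrition, 320 leaves 240, which is 10 fewer (4%) than the 250 behind the power statements.

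The consequence is modest. SEM power falls by 0.15 and 0.63 percentage points and stays above .97; this rests only on stated inputs. Aim 1 power at f = .07 falls by about 1 to 2 points for rho from .3 to .7, and from .80 to .782 at the rho that matches the plan; this rests on the assumed rho and sphericity. The conclusion of adequate power does not change for the SEM. The point should be corrected as an inconsistency in a figure the trial relies on; it is not evidence that the design fails.

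**What to change.** State one target in every section. There are two ways to do it:

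- **Adopt 334.** Replace 320 with 334 in both places in section 3.0 and in section 12.0, and 160/160 with 167/167 in section 3.0. Section 16.0 then stands unchanged.
- **Keep 320.** Restate section 16.0 for 240 completers (120 per group), with SEM power of .995 and .977 and the detectable Aim 1 effect recomputed for N = 240 at a stated rho.

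In either case, say in sections 5.0 and 8.0 that 350 is a ceiling and name the target beside it.

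If enrolment has already closed, restate section 16.0 with the actual number enrolled. Label it as an after-the-fact restatement, and keep the original calculation visible so that it still shows what was planned in advance.

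The cost is a text correction in three places, or a restatement of one section. No design change is needed: 334 is already in the plan and below the stated ceiling.
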